APPENDIX D. NEONATAL INFANT PAIN SCALE (NIPS)

(1) Facial Expression; (2) Cry; (3) Breathing patterns; (4) Arms; (5) Legs; (6) State of Arousal.

Parameter	Finding	Points
Facial expression	Relaxed	0
	Grimace	1
Cry	No Cry	0
	Whimper	1
	Vigorous Cry	2
Breathing Patterns	Relaxed	0
	Change in breathing	1
Arms	Restrained	0
	Relaxed	0
	Flexed	1
	Extended	1
Legs	Restrained	0
	Relaxed	0
	Flexed	1
	Extended	1
State of Arousal	Sleeping	0
	Awake	0
	Fussy	1

Instructions for Use

The NIPS is an observational measure and is administered with the behavioral parameters and possible scores on the Y-axis. Scoring is permitted at one-minute intervals (along the X-axis), and can take place before, during, and after a procedure. The total score for a one-minute interval can range from 0 – 7.

Interpretation

Scores for each category are summed: the minimum score is 0, and the maximum score is 7. The primary limitation is that infants too ill to respond or that are receiving a paralytic agent may produce a falsely low score.

APPENDIX E. BLOOD SAMPLING INSTRUCTIONS

Visit/Phase	Amount Collected	Number of Samples Collected	Total Amount Collected Per Subject
Screening Serum Chemistry and Hematology ^a	1.25 mL	1	1.25 mL
For Subjects with Body Weights 3 - <6 kg			
Single-Dose Phase Pharmacokinetics	0.5 mL ^b	7	3.5 mL
Multiple-Dose Phase Pharmacokinetics	0.5 mL ^b	5	2.5 mL
For Subjects with Body Weights 6 - <10 kg			
Single-Dose Phase Pharmacokinetics	1.2 mL ^c	7	8.4 mL
Multiple-Dose Phase Pharmacokinetics	1.2 mL ^c	5	6.0 mL
For Subjects with Body Weights ≥10 kg			
Single-Dose Phase Pharmacokinetics	1.2 mL ^c	7	8.4 mL
Multiple-Dose Phase Pharmacokinetics	1.2 mL ^c	5	6.0 mL
End of Treatment Serum Chemistry and Hematology	1.25 mL	1	1.25 mL
Grand Total			
Single-Dose Phase for Subjects with Body Weights 3 - <6 kg			6.0 mL ^b
Multiple-Dose Phase for Subjects with Body Weights 3 - <6 kg			5.0 mL ^b
Single-Dose Phase for Subjects with Body Weights 6 - <10 kg			10.9 mL ^c
Multiple-Dose Phase for Subjects with Body Weights 6 - <10 kg			8.5 mL ^c
Single-Dose Phase for Subjects with Body Weights ≥10 kg			10.9 mL ^c
Multiple-Dose Phase for Subjects with Body Weights ≥10 kg			8.5 mL ^c

^a Where possible, results from clinical laboratory tests performed as part of the standard of care (SOC) will be used for study purposes. A separate blood draw for the clinical laboratory test portion of this protocol will occur only if the clinical laboratory tests as part of the SOC will not be available to coincide with approximately the time scheduled by protocol. Preoperative or intraoperative (collected pre-first incision) test results must be available for review by the Investigator prior to dosing any subject. See Table 9 for list of analytes for clinical laboratory tests. Procedures for blood draws should follow institutional SOC. Refer to Table 10 for limitations on blood volumes.

^b For all subjects weighing between 3 and <6 kg, only up to 0.5 mL of discard volume will be allowed.

^c Includes up to 1.0 mL discard volume for all pharmacokinetic (PK) samples; a 0.5 mL discard volume should be used with short tubing (eg, tubing with a dead space of ≤0.5 mL) and up to a 1.0 mL discard volume should be used for longer tubing (eg, tubing with a dead space of >0.5 mL). Total blood volume drawn for research purposes must not exceed 3% of subject's total blood volume, which is assumed to be 75 to 80 mL/kg; the blood volume is higher in the neonatal period (from 85 mL/kg to a peak of 105 mL/kg by the end of the first month, and then decreases progressively over the ensuing months).¹ Refer to Table 10 for limitations on blood volumes.

¹ Howie SR. Blood sample volumes in child health research: review of safe limits. *Bull World Health Organ.* 2011;89(1):46-53.

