13. ASSESSMENT OF PHARMACOKINETICS

13.1. Study Drug Concentration Measurements

13.1.1. Blood Sample Collections

Blood collection may be performed using an existing line (arterial or venous) at the start of the study (the use of EMLA[®] at the insertion site is permitted). If access for blood sampling is lost, a new line will be established only as required for the clinical management of the subject and not solely for study purposes. Procedures for blood draws should follow institutional SOC. All catheter lines should be appropriately flushed per institutional SOC prior to each blood draws. The discard volume must be restricted to 0.5 mL for tubing with a dead space of ≤ 0.5 mL and up to 1.0 mL for tubing with a dead space > 0.5 mL for subjects weighing ≥ 6 kg. For subjects weighing between 3 and < 6 kg, only up to 0.5 mL of discard volume will be allowed.

Calculation and evaluation of the following PK variables only for single-dose administration will be performed for all subjects participating in study: Single-dose Phase - C_{max} , T_{max} , AUC_{0-t} (see Table 11 for definitions).

For subjects with body weights 3 to < 6 kg, 0.5-mL blood samples will be obtained and placed into 2.0-mL dipotassium ethylenediaminetetraacetic acid (K_2EDTA) tubes for the single-dose phase, and 0.5-mL blood samples will be obtained and placed into 2.0-mL K_2EDTA tubes for the multiple-dose phase. For subjects with body weights 6 to < 10 kg, 1.2-mL blood samples will be obtained and placed into 2.0-mL K_2EDTA tubes for the single-dose phase, and 1.2-mL blood samples will be obtained and placed into 2.0-mL K_2EDTA tubes for the multiple-dose phase. For subjects with body weights ≥ 10 kg, 1.2-mL blood samples will be obtained and placed into 2.0-mL K_2EDTA tubes at each blood collection time point for both phases (see Table 3 and Table 4). The samples will be obtained at the times designated in section 3.

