Immediately after collection, the tube will be gently inverted several times to mix the anticoagulant with the blood sample. The plasma fraction will be separated by placing the collection tube into a refrigerated centrifuge ($4^{\circ}C$ to $8^{\circ}C$) for 10 minutes at $1,500 \times g$. The plasma fraction will be withdrawn by pipette and placed into a polypropylene freezing tube in 2 aliquots. All sample collection and freezing tubes will be clearly labeled in a manner that identifies the subject and the collection time. Labels will be fixed to the freezing tubes in a manner that will prevent the label from becoming detached after freezing. All plasma samples will be placed into a freezer at $-70^{\circ}C$ or below within 1 hour after collection. The additional blood draws for the purposes of PK assessment in this study do not pose more than a minor risk to the subjects.

Total blood volume that will be collected for research purposes, including any discard volume, will be based on the age and weight criteria in section 13.1.2.

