13.1.2. Blood Volumes

The total blood volume that will be collected for the study purposes will be limited to 3% (rounded to the nearest mL) of the total blood volume of the study subject based on the criteria in Table 10 and Appendix E (based on Investigator feedback and values reviewed in Aladangady et al and Howie).(30,31) This volume limitation includes discard volume, which should be limited to between 0.5 and 1.0 mL depending upon the dead space of the blood collection tubing (see Appendix E footnotes) for subjects weighing ≥ 6 kg. For subjects weighing between 3 and <6 kg, a discard volume only up to 0.5 mL will be allowed. The blood volume of the study population is estimated to be 75 to 80 mL/kg (human blood volume peaks at 105 mL/kg by the end of the first month, and then decreases progressively over the ensuing months).(31) The minimum weight limit for participation in the study is 3 kg. Refer to Appendix E for required sample volumes for PK analyses.

Table 10: Blood Volumes

Body Weight	Blood Volume (mL/kg)	Total Volume (estimate) (mL)	($\leq 3\%$) Total Volume of Blood Allowed for Study (mL)
3 kg – <6 kg	85	255	7.65 ^a
6 kg – <10 kg	95 ^b	570	17.1 ^a
≥ 10 kg	75	750	22.5 ^a

^a Inclusive of up to 2.5 mL (1.25 mL at screening and 1.25 mL at end-of-treatment) for clinical laboratory testing

^b Blood volume is higher in the neonatal period (from 85 mL/kg to a peak of 105 mL/kg by the end of the first month, and then decreases progressively over the ensuing months).(31) Mean of $(85 + 105 \text{ mL/kg})/2 = 95 \text{ mL/kg}$.

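### For infants of 3 to <6 kg, the Appendix E blood totals leave out discard volume that the 3% limit counts, and footnote b does not say whether its 0.5 mL is per draw or in total

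*Protocol*

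**What the plan says.** For the 3 to <6 kg band, Appendix E lists 7 single-dose or 5 multiple-dose PK samples of 0.5 mL each, plus 1.25 mL of laboratory blood at screening and again at end of treatment. Its grand totals are 6.0 and 5.0 mL. Both carry footnote b: "For all subjects weighing between 3 and <6 kg, only up to 0.5 mL of discard volume will be allowed".

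Section 13.1.1 says of this band that "0.5-mL blood samples will be obtained and placed into 2.0-mL dipotassium" EDTA tubes, so the 0.5 mL is what reaches the tube. The same section requires that "All catheter lines should be appropriately flushed per institutional SOC prior to each blood draws", with the discard limits directly after. It also says what is counted: "Total blood volume that will be collected for research purposes, including any discard volume".

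Section 13.1.2 sets the 3% limit and says: "This volume limitation includes discard volume, which should be limited to between 0.5 and 1.0 mL depending upon the dead space". The 0.5 to 1.0 mL range there is for 6 kg and above; the next sentence gives up to 0.5 mL for smaller infants, again without a unit. Table 10 prints 7.65 mL for 3 to <6 kg (85 mL/kg at 3 kg), and its footnote a describes the caps as "Inclusive of up to 2.5 mL (1.25 mL at screening and 1.25 mL at end-of-treatment) for clinical laboratory testing". The text of 13.1.2 uses a different basis: "The blood volume of the study population is estimated to be 75 to 80 mL/kg". Appendix E footnote c repeats the 75 to 80 mL/kg figure.

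Footnote c, for 6 kg and above, says the volumes include discard. Footnote b does not.

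**The concern.** Sites would plan draws from Appendix E, and the limit they are planning against is a safety limit in very small infants. A grand total that omits a counted component makes the schedule look lighter than it is. At 3 kg, 6.0 mL against 7.65 mL appears to leave comfortable room. Whether that room exists depends on a word that footnote b lacks. If the 0.5 mL is one allowance for the whole study, the schedule fits. If it is 0.5 mL at each PK draw, the full single-dose schedule does not fit at the lowest eligible weights, and the protocol does not say which samples to give up.

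**Working it through.** **Inputs.** PK samples: 7 (single-dose) and 5 (multiple-dose) at 0.5 mL; laboratory blood 2 × 1.25 = 2.5 mL; discard up to 0.5 mL (all Appendix E). Limit: 3% × mL/kg × weight, with 85 mL/kg from Table 10 or 75 to 80 mL/kg from 13.1.2. Minimum weight 3 kg (section 9.1).

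**1. Reproduce the printed totals.**
- Single-dose: 7 × 0.5 + 2.5 = 6.0 mL.
- Multiple-dose: 5 × 0.5 + 2.5 = 5.0 mL.

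Both match exactly with zero discard.

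**2. Could the 0.5 mL already contain discard?** No. Section 13.1.1 puts 0.5 mL in the tube, and taking a 0.5 mL discard out of it would leave no sample.

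**3. Add discard at its ceiling.**

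| Reading | Single-dose (mL) | Multiple-dose (mL) |
|---|---|---|
| One 0.5 mL allowance | 6.0 + 0.5 = 6.5 | 5.0 + 0.5 = 5.5 |
| 0.5 mL at each PK draw | 7 × 1.0 + 2.5 = 9.5 | 5 × 1.0 + 2.5 = 7.5 |
| Also at two separate lab draws | 9.5 + 1.0 = 10.5 | 7.5 + 1.0 = 8.5 |
| Each PK draw, both labs from standard care | 7 × 1.0 = 7.0 | 5 × 1.0 = 5.0 |

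**4. Limit at 3 kg.** 0.03 × 85 × 3 = 7.65 mL; 0.03 × 80 × 3 = 7.20 mL; 0.03 × 75 × 3 = 6.75 mL.

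**5. Weight at which 9.5 mL meets the limit.** 9.5 / 2.55 = 3.73 kg at 85 mL/kg; 9.5 / 2.40 = 3.96 kg at 80; 9.5 / 2.25 = 4.22 kg at 75. Section 13.1.2 rounds the limit to the nearest mL. That does not move these weights, because a limit below 9.5 mL rounds to 9 or less.

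**6. Room for discard at 3 kg, 85 mL/kg, both study labs.** 7.65 − 6.0 = 1.65 mL, or 1.65 / 7 = 0.24 mL per PK draw. Full discard at three draws (1.5 mL) fits; at four (2.0 mL) it does not. With the limit rounded to 8 mL, four fit and five do not.

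**7. Other cases at 3 kg.** One allowance (6.5 mL) fits on every basis. Per-draw discard with both labs from standard care (7.0 mL) fits 7.65 and 7.20 mL but is above 6.75 mL, although equal to it once rounded to 7. Multiple-dose 7.5 mL fits 7.65 mL but not 7.20 or 6.75 mL; it meets the limit from 7.5 / 2.40 = 3.13 kg or 7.5 / 2.25 = 3.33 kg.

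**8. 6 kg and above.** 7 × 1.2 + 2.5 = 10.9 mL and 5 × 1.2 + 2.5 = 8.5 mL, as printed. Footnote c treats the 1.2 mL as including discard, whereas 13.1.1 says "1.2-mL blood samples will be obtained and placed into 2.0-mL" tubes. The two statements need reconciling.

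**The case against.** The strongest reply is that nothing is added up wrongly. The table counts samples, the sums reproduce, footnote b sits on the grand totals themselves, and the discard figure is a ceiling, so the printed totals can be read as amounts before discard. The control that matters is the 3% limit, which expressly includes discard and is repeated in 13.1.2 and footnote c. Footnote a also takes study laboratory blood only where standard-of-care results are unavailable. All of that stands. It does not rescue the totals as a per-subject budget: they are labelled grand totals, they are set against a limit that counts discard, and the parallel footnote for heavier infants says discard is included.

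It can also be said that the ambiguity is thin, because dead space arises at every draw and the discard limits follow directly on the instruction to flush before each one. Per draw is indeed the likelier reading, but the text does not settle it.

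A fair caution applies to the size. The crossing weights depend on which mL/kg figure is used, and Table 10 shows only one cap per band. I scale it to the infant's own weight because 13.1.2 defines the limit by the subject's total blood volume. Taken as a single cap for the band, 7.65 mL would be exceeded by 9.5 mL at every weight in it.

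For 6 kg and above, a reader might infer from footnote c that 1.2 − 1.0 = 0.2 mL is too little blood. The documents do not support that: section 13.1.4 needs only 50 µL of plasma per sample.

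**Conclusion.** The point holds as a minor one. The 3 to <6 kg totals understate the blood drawn whenever discard is taken, by up to 0.5 mL in either phase if it is one allowance, or by up to 3.5 mL (single-dose) and 2.5 mL (multiple-dose) if it is per PK draw. If separate laboratory draws also need discard, add up to 1.0 mL. With per-draw discard at its ceiling and both study labs, the full single-dose schedule exceeds 3% below about 3.7 kg at 85 mL/kg or about 4.2 kg at 75 mL/kg.

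A reader might infer that the protocol permits a breach of the limit, or that enrolled infants were over-sampled. Neither follows. The 3% cap overrides the table, and the documents give no volumes actually drawn and no individual weights. SAP sections 3.1 and 3.1.1 report five subjects in Group B and none in Groups C and D. SAP sections 7.10 and 8 drop the PK analyses, so no planned analysis depends on these totals. The correction now serves the record and any reuse of the protocol.

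**What to change.** - In footnote b, and in the matching sentences of 13.1.1 and 13.1.2, state that the 0.5 mL is per draw, or that it is one total. Say whether laboratory draws also carry discard.
- Restate the 3 to <6 kg grand totals as maxima including discard: 9.5 and 7.5 mL if per PK draw (10.5 and 8.5 mL if laboratory draws count too), or 6.5 and 5.5 mL if one total.
- Use one mL/kg basis per weight band in Table 10, section 13.1.2 and footnote c.
- Add a rule: when the planned total including discard would exceed 3% at the infant's own weight, named single-dose PK draws are omitted first, keeping at least the 3 that section 9.3.1.1 requires for evaluability. This is feasible at 3 kg with both study labs: 5 × 1.0 + 2.5 = 7.5 mL fits 7.65 mL, and 4 × 1.0 + 2.5 = 6.5 mL fits 6.75 mL. With laboratory discard as well, 3 × 1.0 + 3.5 = 6.5 mL still fits 6.75 mL. If a basis of 75 to 80 mL/kg is chosen, or laboratory draws carry discard, the multiple-dose samples need a similar line.
- For 6 kg and above, only clarify whether the 1.2 mL includes discard.

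The cost is a table and footnote correction with no change to design or analysis. The printed maxima become larger, and the smallest infants may give a few fewer PK samples.

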SOC	Standard of care
TBL	Total bilirubin
TEAE	Treatment-emergent adverse event
WBC	White Blood Cell
WHO	World Health Organization

1. INTRODUCTION

This study has been prematurely terminated based on the recommendation of the Independent Data Review Committee (IDMC) on 12-July-2019. Upon reviewing the data, the IDMC indicated that further exposure of infants <2 months old to single doses of oxymorphone is not indicated or appropriate due to the risk of respiratory depression. This Statistical Analysis Plan (SAP) describes the safety analyses to be included in the abbreviated Clinical Study Report (CSR). All the specific information about the study is described in the EN3319-304 Clinical Study Protocol Amendment 5 dated 1 April 2019 (1).

2. STUDY OBJECTIVES

2.1. Primary Objective

The primary objective of this study is to describe the efficacy of oxymorphone HCl in children aged below 2 years (0 to <2 years) for whom an opioid to treat acute moderate to severe postoperative pain of various etiologies may be an appropriate treatment option.

2.2. Secondary Objective

The secondary objectives of this study are:

- To characterize the safety and tolerability of oxymorphone HCl in children aged below 2 years (0 to <2 years) for whom an opioid to treat acute moderate to severe postoperative pain of various etiologies is an appropriate treatment option.
- To characterize the pharmacokinetics (PK) of oxymorphone HCl in children aged below 2 years (0 to <2 years) for whom an opioid to treat acute moderate to severe postoperative pain of various etiologies is an appropriate treatment option.

3. STUDY DESIGN AND MEASURES

3.1. Study Design

This is a Phase 3, post marketing study conducted to meet a Pediatric Research Equity Act (PREA) commitment. The study comprised an open-label, single-dose, dose selection phase and a randomized, double-blinded, active controlled multiple-dose phase to characterize the efficacy, safety, tolerability, and PK of oxymorphone HCl in pediatric subjects with acute moderate to severe postoperative pain for whom an opioid may be determined to be an appropriate treatment option. It is a multicenter study intended to be conducted at up to 25 sites. At the time the study was prematurely stopped, the study was conducted at 3 clinical sites.

The study was designed to be conducted in 2 phases: single-dose phase and multiple-dose phase. The single-dose phase was an open label dose selection phase intended to determine the dose (for each age group) in the multiple-dose phase (Figure 1) based on the recommendation of an IDMC. The multiple-dose phase included a double-blinded assessment of oxymorphone HCl vs. placebo.

Each study phase consisted of the following planned study periods:

- Screening period (within 5 days of surgery)

- Post-surgery evaluation
- Treatment period occurring after surgery
- End-of-treatment (EOT) assessment 24 hours after the last dose of study drug; and
- 2 follow-up contacts (at 3 ±1 and 14 ±2 days after the last dose of study drug).

All subjects were enrolled preoperatively up to 5 days before surgery with the expectation that they would require intravenous (IV) access after surgery and postoperative analgesia with an opioid.

It was intended to enroll subjects sequentially to each of the below mentioned four age groups with recruitment of older infants and toddlers preceding recruitment of the youngest age subjects:

- Group A: 6 months – <2 years (up to and inclusive of 729 days)
- Group B: 61 days – <6 months (up to and inclusive of 179 days)
- Group C: 31 days – 60 days
- Group D: 0 – 30 days

In the single-dose phase, it was planned that up to 3 cohorts of 5 subjects for each age group would receive oxymorphone HCl and in the multiple-dose phase a single cohort of 10 subjects were planned be enrolled to receive study drug or placebo in 1:1 allocation ratio for each age group. However, by the time Group B was to enroll subjects, the study was suspended (only 5 subjects were enrolled in Group B for cohort 1).

It was intended that the study would first enroll the subjects in oldest age group (Group A), and each subsequently younger age group (B, C, and D) would enter the study only after the preceding age group has completed enrollment and the data is reviewed by an IDMC. Each age group must complete their respective single-dose phase and IDMC review before proceeding to the multiple-dose phase.

3.1.1. Dose Selection at Single-Dose Phase

During the single-dose phase, the first cohort of 5 subjects from Group A entering the study were to receive 0.05 mg/kg oxymorphone HCl immediate-release oral liquid. The IDMC reviewed the data from the initial cohort for efficacy, safety, tolerability, and PK and made a recommendation for the dose for the second cohort of subjects from Group A. Each cohort of age groups progressed through the single-dose phase in the same manner until either 3 doses are assessed in the single-dose phase for each age group or as per the IDMC recommendation that an age group can proceed to the multiple-dose phase. The starting dose for the first cohort of subjects of Group B was determined based on IDMC recommendation following review of data from Group A.

Since it was intended to enroll subjects in Groups C and D to receive the IV formulation of oxymorphone HCl, the IDMC was also expected to review the PK modeling data aggregated from Groups A and B to determine the starting dose of Group C, and after its completion, the starting dose of Group D. However, no subjects were enrolled in Groups C and D.

[figure not shown]
3.1.2. Dose Recommendation for Multiple-Dose Phase

It was intended that following the review of data related to the efficacy, safety, tolerability, and PK from the single-dose phase, the IDMC would provide a recommendation for a dose (for each age group) to be carried forth into the double-blind, placebo-controlled multiple-dose phase to assess efficacy of oxymorphone HCl versus placebo. However, by the time Group B was to enroll subjects in single-dose phase, the study was suspended (only 5 subjects were enrolled in Group B for cohort 1).

The multiple-dose phase was to include a double-blinded assessment of oxymorphone HCl versus placebo conducted in the same manner as the single-dose phase (i.e., the same progression of age groups, beginning with Group A, followed by Group B, etc.), but only a single dose level to be tested in each age group (Figure 1). New cohorts of 10 subjects per age group were to be randomized 1:1 to receive study drug as either oxymorphone HCl (N=5 per age group) at the dose established following IDMC review in the single-dose phase or placebo (N=5 per age group) every 4-6 hours PRN.

The multiple-dose phase used the similar age group stratification as used in the single-dose phase. Subjects were randomized to receive either oxymorphone HCl or placebo in a 1:1 ratio.

Figure 1: Study Design

d=Days; IDMC=Independent data monitoring committee; m=Months; PBO=Placebo; SOC=Standard of care; TBD=To be determined; yr=Years

The total duration of the study, excluding screening, for subjects in the open-label, dose-selection phase was approximately 15 days from the first dose of study drug to last follow-up. The total duration of the study, excluding screening, for subjects in the multiple-dose phase was up to 17 days from the first dose of study drug to last follow-up.

Refer to Table 1 and Table 2 below for details of the Schedule of Assessments/Procedures for the Single-Dose phase and Multiple-Dose phase, respectively.

Table 1: Schedule of Assessments/Procedures for the Single-dose Phase

	Pre-Treatment		Baseline Dosing ^c	Postdose (hours)												EOT Assessment	Follow-Ups (Phone)
	Screening (within 5 days of surgery)	Post-Surgery Evaluation ^a		0.5	1.0	1.5	2.0	2.5	3.0	3.5	4.0	5.0	6.0	8.0	24 hours post dose or ET	(3 [±1] and 14 [±2] days post last dose)	
Time relative to dosing (hours)			0	0.5	1.0	1.5	2.0	2.5	3.0	3.5	4.0	5.0	6.0	8.0			
Informed consent	X																
Inclusion/exclusion criteria ^a	X	X															
Demographics	X																
Medical/surgical history ^b		X															
Physical examination		X													X		
12-lead EKG	X																
Study drug administration			X														
Blood sample for pharmacokinetics			X	X ^a		X		X		X		X		X	X		
Vital signs ^d	X	X	X	X	X	X	X		X		X		X	X	X		
Clinical laboratory tests ^e		X													X		
Continuous pulse oximetry		X	X	Monitored Throughout the Study													
Continuous telemetry		X	X	Monitored Throughout the Study													
Respiratory assessment ^f	X	X	X	X	X	X	X		X		X		X	X	X		
Neurological assessment ^g	X	X	X	X	X	X	X		X		X		X	X	X		
Adverse events ^h	X			Monitored Throughout the Study												X	
Prior and concomitant medications ⁱ	X			Monitored Throughout the Study												X	
Pain assessment ^j			X	X	X	X	X	X	X	X	X	X	X	X	X		
Record surgical details ^k		X															
NCA rescue medication ^l										X							
Food consumption ^m										X							

Table 1: Schedule of Assessments/Procedures for the Single-dose Phase (continued)

Footnotes:

- ^a Study eligibility was re-confirmed before the first dose of study drug was administered. All test results were reviewed by the Investigator or designee prior to dosing a subject.
- ^b Subjects were generally healthy as documented in medical history, including a 12-lead electrocardiogram (EKG) as part of the screening assessment.
- ^c See protocol section 8.1.3 and section 8.1.4 for Baseline Dosing Assessment Procedures and NCA Information. All baseline assessment procedures were completed prior to dosing the subject. After subjects in Groups A and B were post-operative and had shown signs of tolerating oral intake their SOC analgesic regimen were to be discontinued and they would enter the single-dose phase of the study. Subjects in Groups A and B were able to tolerate oral intake prior to receiving oxymorphone oral liquid. It was intended that after subjects in Groups C and D were post-operative, and had shown signs of awakening and arousal, their SOC analgesic regimen would be discontinued and they would enter either the single-dose phase of the study.
- ^d Vital signs included heart rate, respiratory rate, blood pressure, and body temperature.
- ^e Clinical laboratory (chemistry, hematology, and urinalysis) assessments were acceptable for study purposes provided they were taken prior to the first surgical incision and assessed by the Investigator prior to administration of the study drug.
- ^f Respiratory assessment Included oxygen saturation.
- ^g Neurological (sedation) assessments were completed using the Modified Ramsay Sedation Scale (Protocol Appendix A).
- ^h Adverse events (AEs) were collected from the time of informed consent through 14 days after the last dose of study drug (**documented telephone follow-up is required**).
- ⁱ Concomitant medications were collected through 14 days after the last dose of study drug (**documented telephone follow-up is required**).
- ^j The FLACC were used for subjects in Groups A and B. The NIPS was planned to be used for subjects in Groups C and D.
- ^k Surgical details includes type of procedure(s), date of procedure(s), surgical start/stop time, and anesthesia/analgesia start and stop time.
- ^l Rescue medication were administered according to an NCA paradigm, with IV morphine sulfate immediately available.³ The dose of NCA rescue medication was based on weight and age according to well-established standards.^{4,5}
- ^m Recording of food consumption from the period 1 hour prior to administration of study drug through EOT assessment; record all times that any food was consumed and what food was consumed (diet-as-tolerated [DAT], DAT-soft, full fluids [FF], clear fluids [CF], water, formula, breast milk)
- ⁿ Blood samples for PK analysis were collected at 0.5 (for subjects with even subject numbers) or 1.0 hour (for subjects with odd subject numbers), and at 2.0, 3.0, 4.0 and 8.0 hours (protocol section 13.1.1). A window of ±10 minutes was allowed.
- Abbreviations: BL=Baseline; EOT=End-of-treatment; ET=Early termination; EKG=Electrocardiogram; NCA=Nurse-controlled anesthesia

Table 2: Schedule of Assessments/Procedures for the Multiple-dose Phase

	Pre-Treatment		Doses 1-5 ^c (up to 18 hours post first dose)		EO T Assessment	Follow-Ups (phone)
	Screening (within 5 days of surgery)	Post-Surgery Evaluation ^b	Baseline ^d	Post Dose Assessments	(24 hours post last dose or EI)	(3 [±1] and 14 [±2] days post last dose)
Informed consent	X					
Inclusion/exclusion criteria	X	X				
Demographics	X					
Medical/surgical history ^e		X				
Physical examination		X			X	
12-lead EKG	X					
Randomization ^f		X				
Study drug administration ^a			X			
Blood sample for pharmacokinetics ^g			X			
Vital signs ^h	X	X	X	See Footnote “i”	X	
Clinical laboratory tests ^j		X			X	
Continuous pulse oximetry		X	X	Monitored throughout the study		
Continuous telemetry		X	X	Monitored throughout the study		
Respiratory assessment ^k	X	X	X	See Footnote “i”	X	
Neurological assessment ^l	X	X	X	See Footnote “i”	X	
Adverse events ^m	X		Monitored Throughout the Study			X
Prior and concomitant medications ⁿ	X		Monitored Throughout the Study			X
Pain assessment ^o			X	See Footnote “o”		
Record surgical details ^p		X				
Food consumption ^q			Monitored Throughout the Study			
NCA rescue medication ^r				X		

Table 2: Schedule of Assessments/Procedures for the Multiple-dose Phase (Continued)

Footnotes:

^a Prior to entering the multiple-dose phase, when subjects in Groups A and B were postoperative, and had shown signs of tolerating oral intake their SOC analgesic regimen were to be discontinued and they would be randomized and enter multiple-dose phase of the study.

It was intended that prior to entering the multiple-dose phase, when subjects in Groups C and D were post-operative, and had shown signs of awakening and arousal, their SOC analgesic regimen would be discontinued and they were to be randomized and enter the multiple-dose phase of the study. The FLACC were used for subjects in Groups A and B. The NIPS was planned to be used for subjects in Groups C and D. All subjects would then be closely monitored for pain and their pain score would be recorded at least hourly until their pain score is ≥ 4 on the FLACC or ≥ 3 on the NIPS, at which time they were administered study drug (oxymorphone HCl immediate release oral liquid for Groups A and B; IV oxymorphone HCl for Groups C and D) or placebo. Subjects in Groups A and B must be able to tolerate oral intake prior to receiving oxymorphone oral liquid. Morphine-NCA (protocol section 8.1.4) would be initiated coincident with but not earlier than study drug/placebo administration, and this time was designated as day 1 time zero.

^b Study eligibility was re-confirmed before the first dose of study drug was administered. All test results were to be reviewed by the Investigator or designee prior to dosing a subject.

^c Subjects were dosed every 4 to 6 hours as needed. Following dose 1, subsequent doses should be administered no less than 4 hours apart, and at least 20 minutes have elapsed since the last bolus NCA rescue. The last dose of study drug would be administered no later than 18 hours post first dose.

^d Back-to-back assessments were not needed between doses (e.g., final hourly assessments for a dose serve as baseline assessments for the next dose).

^e Subject should be generally healthy as documented in medical history, including a 12-lead electrocardiogram (EKG) as part of the screening assessment.

^f Once subjects had cleared to transition to oral pain medication, they were randomized to receive either oxymorphone HCl (oral or IV) or placebo.

^g A pharmacokinetic (PK) sample was just before each dose. The date, time, and dose amount and date and time of sample collection was recorded.

^h Vital signs included heart rate, respiratory rate, blood pressure, and body temperature.

ⁱ Post-dose vital signs, respiratory assessment, and neurological assessment were recorded at 0.5, 1, 2, 3, and 4 hours after administration of first dose of study drug; and at 0.5, 1, and 2 hours after administration of subsequent doses.

^j Clinical laboratory (chemistry, hematology, and urinalysis) assessments were acceptable provided they were taken prior to the first surgical incision and assessed by the Investigator prior to administration of the study drug.

^k Included oxygen saturation, heart rate, and respiratory rate.

^l Neurological (sedation) assessments were completed using the Modified Ramsay Sedation Scale.

^m Adverse events (AEs) were collected from the time of informed consent through 14 days after the last dose of study drug (documented telephone follow-up is required).

ⁿ Concomitant medications were collected through 14 days after the last dose of study drug (documented telephone follow-up is required).

^o After the first dose of study drug, pain was assessed (using FLACC or NIPS, as age appropriate) every half hour throughout the study period until EOT.

^p Surgical details included type of procedure(s), date of procedure(s), surgical start/stop time, and anesthesia/analgesia start and stop time.

^q Recording of food consumption from the period 1 hour prior to administration of study drug through EOS assessment; record all times that any food was consumed and what food was consumed (diet-as-tolerated [DAT], DAT-soft, full fluids [FF], clear fluids [CF], water, formula, breast milk)

^r Rescue medication was administered according to an NCA paradigm, with IV morphine sulfate immediately available.⁶ The dose of NCA rescue medication was based on weight and age according to well-established standards.^{7,8}

Abbreviations: BL=Baseline; EOT=End-of-treatment; ET=Early termination; EKG=Electrocardiogram; NCA=Nurse-controlled anesthesia

